### **7.5.2 Contraception after Rimiducid Infusion**

Patients with child-bearing potential (defined as age  $\geq$  13 years) must either commit to true abstinence from heterosexual contact or agree to use and be able to comply with two-physician approved effective contraception methods for 6 months after the last dose of rimiducid.

## **7.6 Monitoring**

### **7.6.1 Rimiducid Response Monitoring**

Vital signs are recorded prior to rimiducid infusion, and at 15, 30, 60, 120 and 240 minutes (+/- 5 minutes) after start of infusion. Prior to and after administration of rimiducid, research samples should be collected for BPX-501 T cell tracking and PK testing. Samples for PK testing will be processed differently ([Appendix F](#)).

As achievable, and carefully considering patient weight, blood samples should be drawn within 4 hours prior to the initiation of rimiducid infusion; 30 mins after initiation of the infusion; at 2 hours (< 5 min prior to end of the rimiducid infusion), 4 hours, 6 hours, 8 hours, 12 hours, and 24 hours after the initiation of the infusion. Each sample collected out to 24 hours should be split for separate processing. Approximately 0.5 to 1 mL of blood should be processed to plasma and stored at 80°C for later PK analysis of rimiducid. The remaining sample, at least 0.3 mL of blood, should be analyzed locally for prompt CD3+CD19+ T cell analysis. Additional samples, at least 0.3 mL, should be drawn at 48 hours and 7 days (after initiation of infusion of each dose of rimiducid), and then at 14 days, 21 days and 28 days after the final dose of rimiducid, in the event multiple doses are administered, for evaluation of T cell responses only.

### **7.6.2 Gene Therapy Monitoring**

Long-term follow-up is conducted according to FDA and EMA guidelines. Before HSCT and for up to 5-years post stem cell transplant, patients will be evaluated with a physical exam and blood testing as outlined below (see [Table 2](#)) for vector copy number (VCN) and replication competent retrovirus (RCR) every six months. After 5 years, blood samples will be drawn

annually until 15 years after the last BPX-501 administration. Bellicum will inform the site if sample collection can stop for any patient (criteria for this include all post-treatment PCR assays negative for RCR during the first year, and vector no longer present in 2 consecutive results).

**Table 2: Gene Therapy Monitoring Schedule**

Collection Time Point	Clinical Evaluation	Blood (8 mL)
1 year	X	X
18, 24, 30, 36, 42, 48, 54, 60 months	X	X*
Annually from 6 years to 15 years after the last BPX-501 administration	X	X*

*\* Bellicum will inform the site if sample collection can stop for any patient (criteria for this include all post-treatment PCR assays negative for RCR during the first year, and vector no longer present in 2 consecutive results).*

## 7.7 Management of Experimental Drugs

Rimiducid will be infused upon the development of GVHD (per instructions in [Section 7.2](#)).

This protocol will be conducted during the routine clinical care of the patients. All treatments such as critical medications defined as below shall be collected in the EDC database:

- Treatment for GvHD
- Prophylaxis and/or treatment for infectious complications
- Treatments in association with SAEs

Standard supportive care treatments, non-prescription medications/OTCs, NSAIDs, laxatives/stool softeners, vitamins, and herbal supplements will not be collected if they are not protocol-mandated. Anti-viral prophylaxis will be administered per standard site procedures.

Any post-transplantation pharmacological treatment (including steroids, calcineurin inhibitors, Mycophenolate Mofetil (MMF), Methotrexate (MTX), serotherapy) aimed at preventing GVHD will not be allowed unless approved by Medical Monitor/Sponsor.

## 8 TREATMENTS IN ASSOCIATION WITH SAEs EVALUATION CRITERIA

### 8.1 Laboratory Investigations

Lab tests will be performed according to standard institutional procedures. Additional tests will be undertaken as is the standard institutional practice post-transplant.

## 9 RESPONSE AND TOXICITY EVALUATION

### 9.1 Parameters of safety, assessment of AE and SAE during the duration of the study

#### 9.1.1 Safety Parameters and Definitions

Safety assessments will consist of monitoring and recording protocol-defined AEs and SAEs including measurement of protocol-specified hematology, clinical chemistry variables vital signs and other protocol-specified tests that are deemed critical to the safety evaluation of the study drug(s).

The AE grading (severity) scale found in the NCI CTCAE v4.03 will be used for AE reporting. The NCI CTCAE v4.03 can be found:

[http://ctep.cancer.gov/protocolDevelopment/electronic\\_applications/ctc.htm#ctc\\_40](http://ctep.cancer.gov/protocolDevelopment/electronic_applications/ctc.htm#ctc_40).

Bellicum or its designee is responsible for reporting relevant SAEs to the FDA other applicable regulatory authorities and participating investigators in accordance with International Conference on Harmonization (ICH) guidelines, FDA regulations, European Clinical Trials Directive (Directive 2001/20/EC) and/or local regulatory requirements.

#### 9.1.2 Adverse Event

An AE is any unfavorable and unintended sign, symptom, or disease temporally associated with the use of an investigational medicinal product or other protocol-imposed intervention, regardless of attribution.

This includes the following:

1. AEs not previously observed in the subject that emerge during the protocol specified AE reporting period, including signs or symptoms that were not present prior to the AE reporting -period.
2. Pre-existing medical conditions judged by the investigator to have worsened in severity or frequency or changed in character during the protocol-specified AE reporting period.

#### 9.1.3 Serious Adverse Event

An SAE is any AE that is any of the following:

1. Fatal (i.e., the AE actually causes or leads to death)
2. Life threatening (i.e., the AE, in the view of the investigator, places the subject at immediate risk of death)

3. Requires or prolongs inpatient hospitalization
4. Results in persistent or significant disability/incapacity (i.e., the AE results in substantial disruption of the subject's ability to conduct normal life functions)
5. A congenital anomaly/birth defect in a neonate/infant born to a mother exposed to the investigational product(s)
6. Considered a significant medical event by the investigator (e.g., may jeopardize the subject or may require medical/surgical intervention to prevent one of the outcomes listed above)
7. Suspected transmission of infectious agent via a medicinal product

All AEs that meet any of these criteria must be recorded as SAEs, including events that are a normal part of the underlying disease or associated with the general medical management of the patient.

All AEs that do not meet any of the criteria for serious should be regarded as **non-serious AEs**.

The terms “severe” and “serious” are not synonymous. Severity refers to the intensity of an AE (as in mild, moderate, or severe pain); the event itself may be of relatively minor medical significance (such as severe headache). “Serious” is a regulatory definition and is based on subject or event outcome or action criteria usually associated with events that pose a threat to a subject's life or vital functions. Seriousness (not severity) serves as the guide for defining regulatory reporting obligations.

Severity and seriousness should be independently assessed when recording SAEs on the electronic Case Report Form (eCRF).

The investigator is responsible for ensuring that all SAEs (as defined in [Section 7.1](#)) are recorded on the eCRF and reported to the Sponsor in accordance with protocol instructions.

#### **9.1.4 Adverse Event Reporting Period**

After informed consent, all adverse events will be reported as per [Table 3](#) which details the guidance for AE reporting after study treatment has initiated.

**Table 3: Guidance for Adverse Event Reporting**

Event Type	Reporting Period	Additional Requirements
GvHD	All cases of GvHD should be reported regardless of onset date and should	Not applicable

	not be limited to the below AE/SAE reporting period	
AEs (post-IMP)	
 
From the date of BPX-501 infusion until 30 days after administration regardless of causality assessment (including later worsening of events that began during this timeframe).
 
From the date of rimiducid infusion until 30 days after administration regardless of causality assessment.
 
	
 
Report new AEs for up to 15 years if assessed as related to the investigational products BPX-501 and/or rimiducid.
 

SAEs (post-IMP) including Adverse Events of Special Interest*	
 
From the date of BPX-501 infusion until 180 days after administration regardless of causality assessment (including later worsening of events that began during this timeframe).
 
From the date of rimiducid infusion until 30 days after administration regardless of causality assessment.
 
	
 
Report new SAEs for up to 15 years if assessed as related to the investigational products BPX-501 and/or rimiducid.
 
Report diagnosis of any new secondary malignancy regardless of relationship to investigational product for up to 15 years.
 

Pregnancy of patients or partner	
 
12 months after administration of BPX-501 or rimiducid, whichever occurs later.
 
	
 
Report diagnosis of any congenital anomaly in offspring from a study participant or partner for up to 15 years.
 

\* Adverse Events of Special Interest are Grade III-V encephalopathy or neurologic events - these should be reported to the Sponsor expeditiously, irrespective of regulatory seriousness criteria.

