### 9.2.3 Special Reporting Requirements for Neurotoxicity

BPX-501 cells have been documented to enter the CNS. As the significance of this finding is unknown, all CNS events with apparent encephalitis of  $\geq$  Grade 3 severity must be reported to Bellicum- within the 24 hours (SAE reporting timelines).

Refer to [Appendix E](#) for guidelines pertaining to monitoring and management of neurotoxicity.

Record all case details that can be gathered within the reporting timeframe (24 hours) on the Bellicum SAE Report Form and submit the report to [REDACTED]. Follow-up information should be collected on the SAE Report Form as soon as it becomes available and/or upon request.

Guidelines for medical management of neurotoxicity are provided in [Appendix E](#).

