- 14.3.1.5.1 Treatment-Emergent Infection Adverse Events Regardless of Relationship to Study Treatment, by Preferred Term and Maximum Severity
- 14.3.1.5.2 Treatment-Emergent Infection Adverse Events Regardless of Relationship to Study Treatment, by Preferred Term and Maximum Severity
- 14.3.1.5.3 Treatment-Emergent Adverse Events Grades 3-5 Regardless of Relationship to Study Treatment, by System Organ Class, Preferred Term and Maximum Severity
- 14.3.1.5.4 Treatment-Emergent Neurotoxicity Adverse Events Regardless of Relationship to Study Treatment, by Preferred Term and Dose of BPX-501
- 14.3.2.1 Serious Treatment-Emergent Adverse Events Regardless of Relationship to Study Treatment by System Organ Class, Preferred Term, and Dose of BPX-501
- 14.3.2.2 Serious Treatment-Emergent Adverse Events Occurring After AP1903 Administration, by System Organ Class, Preferred Term, and Dose of BPX-501
- 14.3.2.4 Serious Treatment-Emergent Adverse Events Regardless of Relationship to Study Treatment, by System Organ Class, Preferred Term, and Maximum Severity
- 14.3.2.6 Serious Treatment-Emergent Adverse Events Occurring After AP1903 Administration by System Organ Class, Preferred Term, and Maximum Severity

- 14.3.2.7.1 Treatment-Emergent Adverse Events by Malignant or Non-Malignant Disease Type
- 14.3.2.7.2 Serious Treatment-Emergent Adverse Events by Malignant or Non-Malignant Disease Type
- 14.3.2.7.3 Grade 3-5 Treatment-Emergent Adverse Events by Malignant or Non-Malignant Disease Type
- 14.3.2.8 Summary of Deaths
- 14.3.2.9 Summary of Hospitalizations
- 14.3.4.1.1 Infection Adverse Events Requiring Antiviral, Antibacterial or Antifungal Concomitant Medication Use Within 7 Days
- 14.3.4.1.2 Hematology Results Observed by Visit and Change from Baseline
- 14.3.4.1.2 Hematology Results Shift from Baseline
- 14.3.4.2.1 Chemistry Results Observed by Visit and Change from Baseline
- 14.3.4.2.2 Chemistry Results Shift from Baseline
- 14.3.4.3 Vital Signs Observed by Visit and Change from Baseline

Figures:

- 14.2.1.1 Kaplan-Meier Plot of Event-Free Survival
- 14.2.1.2 Kaplan-Meier Parameter Estimates of Event-Free Survival: Sensitivity Analysis for Any Grade 2-4 Acute GvHD
- 14.2.1.3 Kaplan-Meier Parameter Estimates of Event-Free Survival: Sensitivity Analysis on Dosing Window Subgroups
- 14.2.1.4 Kaplan-Meier Parameter Estimates of Event-Free Survival: Sensitivity Analysis for Death from Any Cause

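### Table 3 makes new late Grade III to V neurologic events reportable, in general, only if judged related, and it conflicts with Section 9.2.3 for late encephalitis

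*Protocol*

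**What the plan says.** **Reporting period.** Protocol Section 9.1.4 sends all adverse event reporting after consent to Table 3. The row headed "SAEs (post-IMP) including Adverse Events of Special Interest" has two all-cause periods:

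- "From the date of BPX-501 infusion until 180 days after administration regardless of causality assessment", with the extension "including later worsening of events that began during this timeframe".
- "From the date of rimiducid infusion until 30 days after administration regardless of causality assessment".

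Beyond these the row says: "Report new SAEs for up to 15 years if assessed as related to the investigational products BPX-501 and/or rimiducid". The same row asks for any new secondary malignancy for 15 years whatever its cause. GvHD has its own row, with no limit by onset date.

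**Definition.** The footnote to Table 3 reads: "Adverse Events of Special Interest are Grade III-V encephalopathy or neurologic events". It waives the seriousness test for these events and says nothing about time or causality.

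**Section 9.2.3.** After noting that BPX-501 cells have been found in the CNS, it continues: "As the significance of this finding is unknown, all CNS events with apparent encephalitis of" Grade 3 or higher are to reach the sponsor within 24 hours. It states no time limit and no causality condition.

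**Observation and analysis.** Protocol Table 1 marks a neurological examination and adverse event collection at every visit from Month 9 to year 15. Protocol Section 10.4.6 runs the safety analysis to study end. SAP Section 7.1.1 plans a table titled "Treatment-Emergent Neurotoxicity Adverse Events Regardless of Relationship to Study Treatment, by Preferred Term and Dose of BPX-501". SAP Sections 2 and 4 allow BP-404 data beyond Day 180 to be used, as supportive results.

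**The concern.** BP-404 exists to observe long-term safety, and its neurologic events carry a special-interest label. Yet they follow the ordinary serious-event period, whose BPX-501 part is nearly over when a patient becomes eligible. An investigator who sees a first Grade 3 encephalitis at Month 18, with no recent rimiducid, and rates it unrelated has two instructions: Section 9.2.3 asks for the report and Table 3 does not. For another Grade III to V neurologic event in the same position, no passage asks for the report.

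Two things are at stake. First, late capture would rest mainly on the investigator's causality rating, although the protocol itself calls the significance of CNS entry unknown. Second, if late BP-404 data are put in a table that is titled as all-cause, its early and late parts would have been collected under different rules.

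**Working it through.** The plan states no figure to reproduce. The check is a comparison of passages and some date arithmetic.

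**1. What is reportable late, by type of event.** Take a new-onset event more than 180 days after BPX-501 and more than 30 days after any rimiducid, rated unrelated.

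| Event | Table 3 | Section 9.2.3 | Result |
|---|---|---|---|
| Encephalitis, Grade 3 or higher | Not reportable | Reportable | Conflict |
| Other Grade III to V encephalopathy or neurologic event | Not reportable | Not addressed | Gap |
| Secondary malignancy in the CNS | Reportable for 15 years | Not needed | Covered |

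An event that began within 180 days and worsens later stays reportable under Table 3. If an event of special interest is not serious, the ordinary adverse event row does not help: it also limits late events to related ones.

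**2. When the BPX-501 all-cause period ends.** SAP Section 4.1 gives BPX-501 at Day 14 ± 4 after transplant, or Day 21 ± 14 under some protocol versions. Closing day = BPX-501 day + 180.

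- Day 10 to 18: 10 + 180 = 190, to 18 + 180 = 198.
- Day 7 to 35: 7 + 180 = 187, to 35 + 180 = 215.

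**3. When the first BP-404 visit falls.** Month 9 = 9 × 365.25/12 = day 274. With ± 14 days, this is day 260 to 288. Table 1 does not state its anchor, so both are shown.

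- From transplant: the shortest gap is 260 − 215 = 45 days and the longest is 288 − 187 = 101 days.
- From BPX-501: 260 − 180 = 80 days, to 288 − 180 = 108 days.

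Under either anchor and both dosing windows, the period closes before the visit. Table 1 has 12 visits to month 60 and 10 yearly visits; none of the 22 falls inside the period.

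**4. Share of follow-up.** 15 × 365.25 = 5,479 days. 180/5,479 = 3.3%. The remainder is (5,479 − 180)/365.25 = 14.5 years.

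**5. What is left at entry.** BP-404 takes patients beyond Day 180. If that day is counted from transplant, at most 187 − 180 = 7 to 215 − 180 = 35 days of the period remain.

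**6. How far rimiducid reopens it.** Appendix B describes up to three doses 48 hours apart. The last is then 4 days after the first, and all-cause reporting runs for 4 + 30 = 34 days from the first dose of a full course.

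**The case against.** **Section 9.2.3 may set speed, not period.** It sits under expedited reporting, and Section 9.2.4 likewise asks for all serious events within 24 hours without repeating Table 3's limits. On that reading the sections complement each other. This is a fair reading, but Section 9.2.3 does not say so, and it gives a reason that does not expire at 180 days. Both readings remain open, and the passages must be reconciled. Even on the speed reading, the definitions differ and the Table 3 gap remains.

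**The tiered scheme looks deliberate.** The 180 days match the parent study's minimum follow-up, and all-cause early with related-only late is a coherent plan. That stands as a description. However, GvHD and secondary malignancy are exempted from it and the events of special interest are not, without a stated reason.

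**Stronger readings that the documents do not support:**

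- A reader might infer that all late neurotoxicity is captured only if related. Later worsening, the 30 days after rimiducid (which Appendix E allows for neurotoxicity), secondary malignancy and Section 9.2.3 itself are other routes.
- A reader might infer that Table 3 contradicts Section 9.2.3 for every event of special interest. The overlap is encephalitis only.
- A reader might infer from the visit dates that nothing can be reported all-cause in BP-404. Reporting follows events, not visits: an event that began inside the period and is found at Month 9 still belongs to it.
- A reader might infer that the planned neurotoxicity table is biased by a known amount. The SAP is written for BP-004, its primary analysis is at 180 days, and later data are supportive.
- A reader might infer that causality cannot be judged. The protocol calls the significance of CNS entry unknown, which is less than that, and Appendix E describes a work-up that would inform the judgement.

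**Conclusion.** The point holds within these limits. Under Table 3, a new-onset Grade III to V encephalopathy or neurologic event more than 180 days after BPX-501 and more than 30 days after any rimiducid is reportable only if assessed as related, unless it is a secondary malignancy. For late encephalitis rated unrelated, this conflicts with Section 9.2.3 as worded. For the other neurologic events of special interest it is an omission in Table 3.

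In time, the restriction covers about 14.5 of 15 years, apart from 30 days after each rimiducid dose, and it starts before the first scheduled visit. In events, the size is unknown: the documents give no rate of late neurologic events and no share that would be rated unrelated. The dates assume the dosing windows in SAP Section 4.1; their order does not depend on Table 1's anchor.

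The effect on the SAP table is conditional. If post-Day-180 data enter it, all-cause early events would stand beside mostly related-only late events under an all-cause title. The point should be settled by amendment; it does not affect the survival endpoints.

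**What to change.** 1. In Table 3, take the adverse events of special interest out of the serious-event row and give them their own row, reported regardless of causality during BP-404 follow-up, as is already done for GvHD and secondary malignancy.
2. Use one event definition in Table 3 and Section 9.2.3, naming encephalitis, encephalopathy and other neurologic events explicitly. State in Section 9.2.3 that its 24 hours is the reporting speed and that Table 3 gives the period.
3. If late BP-404 data are shown in the neurotoxicity table, state in a footnote which reporting rule applied in each period. This also covers data collected before the amendment.

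The cost is amendment text and some additional event reports over 15 years in up to 175 patients, including relapsed patients who stay in follow-up. That number cannot be estimated from the documents. No new procedures are needed, because the neurological examinations are already scheduled.

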### 9.1.5 GVHD Adverse Event Reporting

All occurrences of GVHD will be reported as Adverse Events (or SAEs) regardless of their start date in relation to study treatment. GVHD events will also be followed until resolution and not limited to the standard AE/SAE reporting period.

## 9.2 Expedited Reporting Requirements for Serious Adverse Events

### 9.2.1 Reporting Requirements for Fatal/Life-Threatening SAEs Related to Investigational Product

Any life-threatening or fatal SAE that is attributed by the investigators to the investigational product will be telephoned to the Medical Monitor immediately, followed by submission of written case details on a CRF within 24 hours.

### 9.2.2 Reporting SAEs to the IRB or Ethics Committee and Regulatory Authorities

The investigator must comply with the applicable regulatory requirements related to the reporting of SAEs to the required ECs or IRBs.

All events qualifying as Suspected Unexpected Serious Adverse Reactions (SUSARs) will be reported to the relevant regulatory authorities, central Ethics Committees and to EudraVigilance by the Sponsor or its representative. SUSARs are required to be reported within 7 calendar days for life threatening events and those resulting in death, or 15 calendar days for all others. These timeframes begin with the first notification of the SUSAR to the Sponsor from the investigator.

### 9.2.3 Special Reporting Requirements for Neurotoxicity

BPX-501 cells have been documented to enter the CNS. As the significance of this finding is unknown, all CNS events with apparent encephalitis of  $\geq$  Grade 3 severity must be reported to Bellicum- within the 24 hours (SAE reporting timelines).

Refer to [Appendix E](#) for guidelines pertaining to monitoring and management of neurotoxicity.

Record all case details that can be gathered within the reporting timeframe (24 hours) on the Bellicum SAE Report Form and submit the report to [REDACTED]. Follow-up information should be collected on the SAE Report Form as soon as it becomes available and/or upon request.

Guidelines for medical management of neurotoxicity are provided in [Appendix E](#).

